STUDY PROPOSAL

**A PHARMACOEPIDEMOLOGICAL STUDY ON THE INTERACTION
BETWEEN CLOPIDOGREL AND PROTON PUMP INHIBITORS AND
THE RISK OF ACUTE MYOCARDIAL INFARCTION , CORONARY
HEART DISEASE DEATH AND UPPER GASTROINTESTINAL
BLEEDING IN THE GPRD AND THIN DATABASES**

Confidential: This study is supported by an unrestricted research grant from AstraZeneca

BACKGROUND

Clopidogrel is a thienopyridine with platelet inhibitory properties that selectively inhibits adenosine diphosphate (ADP)-induced platelet aggregation with no direct effects on arachidonic acid metabolism (1). Although clopidogrel also can inhibit platelet aggregation induced by collagen and thrombin, these inhibitory effects are abolished by increasing the agonist concentration and, therefore, are likely to reflect blockade of ADP-mediated amplification of the platelet response to other agonists. Clopidogrel is a prodrug that suffers in vivo hepatic transformation mediated mainly by cytochrome P-450 isoenzymes to generate an active metabolite, that irreversibly inhibits the platelet P2Y₁₂ ADP receptor. The active metabolite of clopidogrel has a pharmacodynamic pattern quite similar to that of aspirin, in causing the cumulative inhibition of platelet function on repeated daily administration of low doses with platelet function returning to normal 7 days after the last dose of clopidogrel. This also justifies the once-daily regimen of clopidogrel despite its short half-life in the human circulation. Clopidogrel, along with aspirin therapy, is now widely used around the world to prevent thrombotic events in patients with acute coronary syndromes and after coronary artery stenting.

The inhibition of gastric acid secretion is a key therapeutic target for peptic ulcer, gastro esophageal reflux disease (GERD) and nonsteroidal anti-inflammatory drug-induced gastropathy among other acid-related diseases. Currently this is mainly achieved by blocking the effects of acid secretagogues through the use of irreversible H⁺/K⁺-ATPase inhibitors commonly referred to as proton pump inhibitors (PPIs). PPIs are potent acid suppressants and are the one drug class most widely used. All of them undergo extensive hepatic biotransformation.

The isoenzyme CYP2C19 seems to be one of the determinants of the pharmacodynamic response to clopidogrel (2,3), and is also involved in the metabolism of PPIs (4), though other CYP isoenzymes (CYP2C9: used in the

metabolism of NSAIDs such as naproxen, ibuprofen or celecoxib) have been reported as affecting platelet responsiveness to clopidogrel (3). In a recent randomized, double-blind, placebo-controlled study (5), the authors suggest a potential clopidogrel–omeprazole drug interaction at the CYP2C19 level. In their study of patients undergoing elective coronary stenting, co-administration of omeprazole with clopidogrel was associated with significantly higher platelet P2Y12 reactivity as measured by a flow cytometry assay employing monoclonal antibodies specific for vasodilator-stimulated phosphoprotein phosphorylation (VASP-P): all clopidogrel patients were also taking aspirin. These results support the findings from their prior observational study (6). In another pharmacodynamic study addressing the interaction between PPIs and clopidogrel, the authors found no association with esomeprazole and pantoprazole (7). At the same time, two observational studies have reported an increased risk of myocardial infarction (MI)/acute coronary syndrome (ACS) among concomitant users of clopidogrel and PPI (8,9). A third observational study using a population-based registry of MI patients reported that the use of omeprazole, or any other proton-pump inhibitor, had no effect on the clinical response (death from any cause, nonfatal stroke, or myocardial infarction) to clopidogrel over one year follow-up (10).

The current study protocol is designed with the aim to address methodological shortcomings in published epidemiological studies, in particular the absence of data on the occurrence of cardiovascular (CV) and upper gastrointestinal (UGI) events in one single population through:

- Evaluating both CV and GI risks in the same population-based cohort (not only CV as in published studies)
- Controlling for differences in "base-line risk" between study groups i.e. to allow adjustment for relevant confounding factors like smoking habits lacking in published observational studies
- Providing information on life style factors like BMI, alcohol use lacking in published observational studies

- Optimizing selection of truly population-based datasources to allow for evaluation of dual clopidogrel and acetylsalicylic acid (ASA) treatment (extensive over-the counter use of ASA not accounted for in published studies)

This study proposal will address separately the risk of two outcomes in a cohort of patients discharged after a hospitalization for acute serious coronary heart disease:

THIN covers about 5% of the UK population, and is age-, gender-, and geographically representative. Data from approximately 4 million patients are systematically recorded by participating general practitioners and sent anonymously to THIN. THIN collects and organizes this information in order to be used for research projects. The computerized information includes demographics, details from general practitioner's visits, diagnoses from specialist's referrals and hospital admissions, results of laboratory tests and a free text section. Prescriptions issued by the general practitioner are directly generated from the computer.

The READ classification is used to code specific diagnoses, and a drug dictionary based on data from the MULTILEX classification is used to code drugs in both databases.

Ascertainment of study cohort

Follow up will start on the first day after _____ once an individual meets the criteria of at least one year enrollment with the general practitioner, one year since first computerized prescription and being 50-84 years old. That date will be their start date¹. We will exclude patients with a recorded diagnosis of cancer before start date¹. We will also remove from the source population all persons aged 70 and above with a follow-up longer than one year and less than 2 health contacts during their total follow-up

(proxy for incomplete data recording). Follow-up will end on the first of the following:

1. The date of a qualifying event; which is a hospitalization for acute serious coronary heart disease: defined as acute myocardial infarction, revascularization of the coronary arteries, or unstable angina.
2. The attainment of age 85;
3. The date of recorded diagnosis of cancer;
4. The date of death;
- 5.

We will review computer profiles of all persons identified with a serious coronary heart disease (free text comments will not be requested at this stage) and will retain as our study cohort all patients with documented evidence of hospitalization for acute serious coronary heart disease and who are alive one month after the qualifying hospitalization (start date2).

AMI and CHD death: case ascertainment and validation

We will follow-up all study cohort members from start date2 until the earliest occurrence of one of the following endpoints:

1. The date of a code suggesting a hospitalization for acute myocardial infarction
2. The attainment of age 85;
3. The date of recorded diagnosis of cancer;
4. The date of death;
- 5.

We will manually review computerized profiles of all patients with a code suggesting MI as well as deceased patients: free text comments will be requested before reviewing patient profiles. All patient personal identifiers will be suppressed. At this stage, we will exclude patients not admitted to a hospital and patients with a hospitalization for a non IHD event in the previous month. For a random sample of 100 potential cases of AMI in each

database, we will send a questionnaire to the GPs in order to confirm the diagnosis of AMI and request all information available in their office related to the episode of AMI including hospital discharge letters, electrocardiograms (ECGs), or results from myocardial serum enzyme levels . To validate cases we will use the adapted international standardised diagnostic criteria for acute myocardial infarction (11,12). We will apply the same methods of case ascertainment and validation for AMI as described in our two recent studies, one using the GPRD (13) and the second with THIN (14). In these two studies, we obtained a confirmation rate close to 95 % among the requested random sample of patients considered cases after the manual review. If based on the information from the questionnaire and medical records, 90% or more are confirmed as cases of AMI, we will not request information for all remaining potential cases.

Also, we will review all deaths and consider a patient as dying from coronary heart disease (CHD) when there is a) postmortem evidence of fresh MI, b) a recent coronary artery occlusion or ante-mortem evidence of CHD in the absence of another cause of death, or c) recorded CHD as the underlying cause of death. We will consider as cases of CHD death patients who died from CHD before reaching the hospital as well as fatal AMI (patients dying within the first 30 days after the occurrence of AMI).

UGIB: case ascertainment and validation

In addition to cancer we will remove from our study cohort for UGIB ascertainment all individuals with a recorded history of oesophageal varices, Mallory-Weiss disease, alcoholism, chronic liver disease or coagulopathies prior to start date2. Then, we will follow-up all study cohort members from start date2 until the earliest occurrence of one of the following endpoints:

1. The date of a code suggesting an episode of UGIB
2. The attainment of age 85;
3. The date of exclusion factor occurrence: codes for cancer, oesophageal varices, Mallory-Weiss disease, alcoholism, chronic liver disease or coagulopathies.
4. The date of death;
- 5.

We will manually review computerized profiles of all patients with a code suggesting UGIB: free text comments will be requested before reviewing patient profiles. All patient personal identifiers will be suppressed. At this stage, we will exclude patients with a hospitalization for a non UGI event in the previous month. We will consider a patient to be a case of UGIB when no exclusion criterion is found, the specific site of the bleed/perforation is located in the stomach or duodenum or the clinical diagnosis is peptic ulcer, and the patient has been referred to a consultant or admitted to hospital. We will classify cases according to the source of the bleed/perforation into gastric and duodenal. Subjects with any of the exclusion criteria mentioned above in the 2 months after the date of case detection (index date), and subjects with the source of the bleed/perforation in the esophagus or lower gastrointestinal tract will be excluded. The date of first objective sign of the bleed episode will be considered as index date. To validate the case status based on the review of computerized patient profiles, we will send the general practitioners for a random sample of 100 potential UGIB cases in each database, a questionnaire and a request to send all the information related to that event. We will apply the same methods of case ascertainment

and validation for UGIB as described in two of our studies, one using the GPRD (15) and the second with THIN (16). In these two studies, we obtained a confirmation rate close to 95 % among the requested random sample of patients considered cases after the manual review. If based on the information from the questionnaire and medical records, 90% or more are confirmed as cases of UGIB, we will not request information for all remaining potential cases.

Statistical analysis

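### Follow-up for both outcomes ends at the first unconfirmed code, and nothing returns the patient to follow-up when review rejects that code

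*Protocol*

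**What the plan says.** Under Ascertainment of study cohort, patients enter after "a hospitalization for acute serious coronary heart disease: defined as acute myocardial infarction, revascularization of the coronary arteries, or unstable angina". The study cohort is those "who are alive one month after the qualifying hospitalization (start date2"), so observation for outcomes begins one month after that hospitalization.

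Under AMI and CHD death: case ascertainment and validation, the first listed end of follow-up is "The date of a code suggesting a hospitalization for acute myocardial infarction". Under UGIB: case ascertainment and validation, it is "The date of a code suggesting an episode of UGIB". Neither is conditional on confirmation.

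Review follows. For AMI, "free text comments will be requested before reviewing patient profiles", and two groups are then excluded: patients not admitted, and "patients with a hospitalization for a non IHD event in the previous month". A random sample of 100 potential cases per database goes to the GP for confirmation, and validation stops there if 90% or more are confirmed. The Protocol expects this to succeed because in earlier studies "we obtained a confirmation rate close to 95 % among the requested random sample of patients considered cases after the manual review".

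Under Statistical analysis, confirmed cases take the admission or onset date as index date. Controls are eligible only if their random date falls between start date2 and the end of follow-up.

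**The concern.** A suggestive code is a screening signal; the confirmed event is the outcome. Letting the signal end observation means that every false signal removes a patient who is still at risk. A true AMI or UGIB after a rejected code lies outside follow-up, and no control can be drawn from that time.

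The AMI outcome is more vulnerable than UGIB. Entry event and outcome can be the same diagnosis in the same GP record, one month apart. A late or repeated entry for the qualifying admission can look like a suggestive code. Better review does not help: the more old AMIs it rejects, the more patients have already left follow-up.

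UGIB has no carried-over entry event, but it has the same missing rule. Review rejects bleeds sited in the oesophagus or lower tract and patients neither referred nor admitted, and those codes too will have ended follow-up.

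**Working it through.** **1. The plan's own figures** (Power calculation).
- Person-years: 25,000 × 4 = 100,000.
- Cases: 100,000 × 0.02 = 2,000 AMI/CHD; 100,000 × 0.01 = 1,000 UGIB.
- Clopidogrel-exposed cases: 2,000 × 0.40 = 800; 1,000 × 0.40 = 400.
- Power, comparing PPI use in exposed cases with 40% in controls, five controls per case, one-sided 5%. For 1.25 the odds in cases are 1.25 × 0.40/0.60 = 0.833, so the proportion is 0.4545 and power is 0.886. For 0.75 the odds are 0.50, the proportion 0.3333 and power 0.809. Both exceed 80%, as stated.

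**2. What the documents give on rejected codes.** Nothing. The 95% figure describes patients already accepted at manual review, so it does not say how many coded patients were rejected. For AMI, the titles of both cited studies place them in the general population, not in a cohort selected for a recent coronary admission.

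**3. AMI/CHD cases lost if re-recorded codes are rejected.** Assumptions, none from the documents: a share a of the cohort qualifies by AMI, a share r of those gets a repeat code that meets the end-point wording, and 3.5 of the 4 years remain.

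Lost cases = 25,000 × a × r × 3.5 × 0.02

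| a | r | patients | person-years | cases lost | share of 2,000 |
|---|---|---|---|---|---|
| 30% | 5% | 375 | 1,312.5 | 26 | 1.3% |
| 50% | 10% | 1,250 | 4,375 | 88 | 4.4% |
| 70% | 20% | 3,500 | 12,250 | 245 | 12.3% |

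This treats every repeat code as rejected, and applies the 2% rate, which covers CHD deaths as well as AMI.

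**4. Effect on power, AMI/CHD.** After a 10% loss, 1,800 cases (720 exposed) give power 0.856. After a 20% loss, 1,600 cases (640 exposed) give 0.818. The range in step 3 stays above 80%.

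**5. UGIB.** No rate of rejected codes is available, so no loss is estimated. The margin is thin: by the same formula 390 exposed cases are needed for 80%, against 400 expected, so a loss above 10/400 = 2.5% would use it up.

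**6. Lesser branch: the qualifying AMI accepted as a case.** If a share s of accepted cases were old AMIs with PPI use as in controls, the proportion in cases would be (1 − s) × 0.4545 + s × 0.40. For s = 5%, 10% and 20%, a true odds ratio of 1.25 would be seen as 1.24, 1.22 and 1.20. These values of s are illustrative; step 6 is an alternative to step 3 for any one code, not an addition to it.

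**The case against.** A reader might go further and infer that qualifying AMIs will be counted as recurrences, so that the outcome is contaminated. The documents do not support that:
- The index date is the admission or onset date. For a re-recorded qualifying AMI, that date precedes start date2 and so falls outside observation.
- Every coded profile is reviewed with free text, and the GP questionnaire requests discharge letters, ECGs and enzyme results for the episode, which would help to date it.
- Estimates are adjusted for follow-up time and for AMI, which would reduce any distortion from false events clustering early.

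What remains is narrower. No sentence expressly requires a separate admission, neither AMI review exclusion removes an old AMI (the patient was admitted, and the event was ischaemic), and an old AMI would satisfy the diagnostic criteria behind the 90% rule.

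Three objections bear on early ending itself:
- The end point is a code suggesting a hospitalization for AMI, not any mention of AMI, so routine references to an old infarction may not trigger it. This is fair, and it argues for the lower part of the assumed range.
- Case time and control time are removed together, so the cost is mainly precision; bias would need false codes related to both exposure and risk. This stands, and no such relation is shown.
- CHD deaths may not be lost, because the Protocol says that all deaths are reviewed. This is partly right. But if a death after a rejected code were counted, that case would come from person-time that cannot supply controls. The text leaves this open.

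**Conclusion.** The point holds as a gap in the follow-up rule for both outcomes. Follow-up ends at an unconfirmed code, nothing resumes it after rejection, and control sampling stops at the same date. For AMI/CHD death the loss is about 26 to 245 of 2,000 expected cases, resting wholly on assumed rates (30–70% entering by AMI, 5–20% of them re-coded, 3.5 years remaining) and on all repeat codes being rejected. It is smaller if later CHD deaths are recovered. For UGIB the rule is the same, but its effect cannot be sized.

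The consequence is mainly lost cases and precision, not demonstrated bias. No stated sample-size or power figure is wrong, and the AMI/CHD power claim survives the range examined. Miscounting of the qualifying AMI is possible on the wording but is largely guarded against by the index-date rule and the review.

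**What to change.** - For both outcomes, end follow-up at the first event confirmed on profile review. State that a patient whose code is rejected continues in follow-up and stays eligible as a control.
- For AMI, state that a case needs an admission separate from the qualifying one and dated after start date2. Ask for that admission date in the GP questionnaire, and count only such events toward the 90% confirmation rule.
- State that CHD deaths after a rejected code count as cases, which is consistent once follow-up continues.

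The cost is Protocol wording and one questionnaire item, since all profiles with a suggestive code are already to be reviewed. The downside is a second profile review for patients who have a rejected code and then a later one.

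### In a cohort defined by prior CHD, a pre-hospital death with no other cause found counts as a CHD death on cohort membership alone, and the same section also tells the review to exclude patients not admitted to hospital

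*Protocol*

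**What the plan says.** **Cohort entry** (Protocol, Ascertainment of study cohort). The study cohort consists of patients with "documented evidence of hospitalization for acute serious coronary heart disease and who are alive one month after the qualifying hospitalization". The qualifying event is "defined as acute myocardial infarction, revascularization of the coronary arteries, or unstable angina".

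**Case review** (Protocol, AMI and CHD death: case ascertainment and validation). The first step reads: "We will manually review computerized profiles of all patients with a code suggesting MI as well as deceased patients". Free text is obtained for this review. The section continues: "At this stage, we will exclude patients not admitted to a hospital". Patients with a non-IHD hospitalization in the preceding month are excluded as well.

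**CHD death** (same section). All deaths are reviewed against three criteria: (a) fresh MI at post-mortem, (b) "a recent coronary artery occlusion or ante-mortem evidence of CHD in the absence of another cause of death", or (c) CHD recorded as the underlying cause. The deaths that count as cases are "patients who died from CHD before reaching the hospital as well as fatal AMI", the latter meaning death within 30 days of an AMI.

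**Validation** (same section). A GP questionnaire goes out for a random sample of 100 potential AMI cases per database. The diagnostic criteria, the past confirmation rate near 95% and the 90% threshold for not requesting the remaining records all concern AMI. No corresponding step is described for CHD deaths.

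**The concern.** There are two faults in one outcome definition.

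First, evidence of CHD during life helps to assign a cause of death only if some people lack it. Here everyone has it by design, and criterion (b) attaches no recency, symptom or timing condition to it. The rule then attributes to CHD whatever the reviewer cannot attribute elsewhere. This affects mainly pre-hospital deaths, which have no terminal admission to supply an ECG, enzymes or a discharge letter.

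Second, two sentences in the section conflict on whether pre-hospital deaths are in the endpoint at all. The same protocol is to be run in two databases, so the text could be applied in two ways.

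At stake is the specificity of the AMI/CHD-death outcome. Non-CHD deaths counted as cases dilute a real PPI effect if they are unrelated to PPI use. If PPI users are frailer, they push a direct PPI comparison upward.

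**Working it through.** **1. Criterion (b) against cohort entry**

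| Step | Source | Consequence |
|---|---|---|
| Entry needs a documented hospitalization for AMI, revascularization or unstable angina | Ascertainment of study cohort | Every member has ante-mortem evidence of CHD at the start of outcome follow-up |
| (b) needs ante-mortem CHD and no other cause | AMI and CHD death section | The first condition is always true; only the second still screens |
| Counted deaths are pre-hospital CHD deaths and fatal AMI | Same section | Fatal AMI rests on the AMI itself, so the default acts on pre-hospital deaths |

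**2. The two hospital sentences**

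The review population includes the deceased, and the exclusion of patients not admitted is stated for that review without qualification. Read literally, it removes "patients who died from CHD before reaching the hospital", whom the endpoint includes. Read as applying only to MI-coded survivors, it leaves those deaths in and the default in step 1 operates. The text does not say which is meant.

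**3. The plan's own figures** (Power calculation)

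- 25,000 × 4 years = 100,000 person-years; × 2% = 2,000 MI/CHD-death cases; × 40% = 800 clopidogrel-exposed cases.
- PPI prevalence among clopidogrel users is 40%, so p0 = 0.40. For a rate ratio of 1.25, p1 = 1.25 × 0.40 / (0.60 + 1.25 × 0.40) = 0.4545.
- A two-proportion comparison with 5 controls per case and one-sided 5% alpha gives 88.6% power. The stated power above 80% reproduces.

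**4. Sensitivity to misclassified deaths**

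The protocol does not give the share of non-CHD deaths among composite cases. I assume s = 10–30% of all composite cases among clopidogrel users. Let R be the true PPI rate ratio for AMI/CHD death, k the PPI rate ratio for the misclassified deaths, and s0 their share among cases not on a PPI. With 40% PPI use:

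- s = s0(0.6 + 0.4k) / [s0(0.6 + 0.4k) + (1 − s0)(0.6 + 0.4R)]
- observed ratio = (1 − s0)R + s0·k

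| R | k (assumed) | s (assumed) | s0 | Observed ratio |
|---|---|---|---|---|
| 1.25 | 1.0 | 10% | 0.109 | 1.223 |
| 1.25 | 1.0 | 30% | 0.320 | 1.170 |
| 1.00 | 1.3 | 10% | 0.090 | 1.027 |
| 1.00 | 2.0 | 30% | 0.234 | 1.234 |

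For the last row: 0.30 = 1.4·s0 / (1 + 0.4·s0), so s0 = 0.30/1.28 = 0.234 and the ratio is 1 + 0.234 = 1.234. If s is instead read as the share among cases not on a PPI, the first two rows become 1.225 and 1.175.

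**5. Power under dilution (k = 1)**

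With exposed cases held at 800 in total, power falls from 88.6% to 82.3% at s = 10% and 64.0% at s = 30%. If the misclassified deaths are added to 800 true cases, with 4,000 controls fixed and the share taken among cases not on a PPI, it is 85.6% at 10% (889 cases) and 76.8% at 30% (1,143 cases).

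**6. Effect on RERI**

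Suppose the misclassified deaths have PPI rate ratio k with or without clopidogrel, and clopidogrel rate ratio 1. Their RERI is k − (k + 1 − 1) = 0. The composite's RERI is then the true RERI multiplied by the correctly classified share of cases in the group exposed to neither drug. It is diluted but not created.

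**The case against.** The strongest defence is that much of the definition still screens. The absence of another cause is a real condition, judged at a manual review with free text, and need not mean a blank cause field. Deaths after a recent non-IHD admission drop out, follow-up ends at a cancer diagnosis or at age 85, and only pre-hospital CHD deaths and fatal AMI count. All of this stands. A reader might infer that every member meets criterion (b), that any death without a recorded cause becomes a case, or that nothing checks these deaths. The documents support none of these. What is missing is external validation.

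A reader might also infer that the rule was taken over from general-population studies. The protocol ties its earlier studies to AMI ascertainment and cites no source for the death criteria, so that cannot be shown.

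On size, it is tempting to say that the bias spans the 1.25 the study is sized to detect. Reading a 30% share as applying to cases not on a PPI gives 0.7 × 1 + 0.3 × 2.0 = 1.30. With the share defined over all composite cases, the worst corner is 1.23. A k of 2.0 would also have to survive the planned adjustment for GP visits, referrals, COPD, diabetes and other covariates.

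The RERI argument stands too, within its assumptions: a PPI-related frailty effect alone produces no additive interaction. A false RERI would need confounding that differs by clopidogrel use.

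Finally, attributing an unexplained pre-hospital death to CHD is a defensible choice in this cohort, because it keeps unwitnessed sudden coronary deaths. Censoring them in the primary analysis would be a trade-off, not a correction.

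None of this makes prior CHD informative here, and none of it reconciles the two hospital sentences.

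**Conclusion.** The point holds in a limited form. The ante-mortem limb of criterion (b) cannot discriminate in this cohort, so a pre-hospital death with no other cause found is a CHD death by cohort membership, without described external validation. Separately, the section contradicts itself on whether such deaths are in the endpoint. The contradiction needs no assumption: read literally, it removes a defined part of the outcome.

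The numerical consequence is conditional on assumed shares of 10–30%. A true 1.25 would appear as about 1.17–1.22 if the misclassified deaths are unrelated to PPI use. A true null would appear as about 1.03–1.23 in a direct PPI comparison if their PPI rate ratio is 1.3–2.0. The direction is therefore not fixed, and the second result does not carry over to RERI. This does not show that the primary definition must be replaced or that a false interaction is to be expected.

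**What to change.** 1. Limit the exclusion of patients not admitted to hospital to non-fatal AMI, so that it no longer removes the pre-hospital CHD deaths that the endpoint includes.
2. At the planned manual review, record each CHD death as definite (post-mortem evidence of fresh MI, recent coronary occlusion, or CHD as the recorded underlying cause) or possible (prior CHD only, no other cause found).
3. Tabulate possible CHD deaths by clopidogrel and PPI exposure.
4. Repeat the AMI/CHD-death analysis without the possible deaths as a sensitivity analysis. The primary definition may stay as it is.

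The cost is protocol wording, one extra field in a review already planned, and one extra analysis with fewer cases and so less precision.
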